9.1. Statistical Hypothesis

The primary statistical hypothesis is that prophylactic treatment with Neumifil will significantly reduce the incidence and/or the severity of symptomatic influenza infection after influenza viral challenge when compared to placebo. Individual comparisons of each Neumifil dose arm to the placebo arm will be performed with an exploratory purpose. No adjustment for multiple comparisons will be performed.

9.2. Sample Size Determination

The sample size is based on the primary comparison of the 2 active treatment arms pooled to the placebo arm. The study has not been powered for the comparisons between each active treatment arm to the placebo arm and these comparisons will be presented for exploratory purposes. Nevertheless, for some of the endpoints, a power above 80% is achieved for these comparisons.

The number of 40 participants in the placebo arm and 60 (30 in each dose arm) in the pooled Neumifil group selected for this study will provide a power of at least 80% to detect a significant reduction in the primary endpoints:

- of 70% compared to the placebo arm in symptomatic influenza infection rate, assuming a symptomatic infection rate of 27.8% in the placebo arm,
- of 65% compared to the placebo arm in peak TSS, assuming a coefficient of variation (CV) of 125%,

using a 1-sided 0.05 type-one error rate for each of the 2 comparisons, without adjustment for multiple testing.

The table below summarises the power achieved with 40 versus 60 participants (for the placebo and pooled active treatment arms, respectively) for the 2 primary endpoints and some secondary endpoints.

Endpoint	Assumption (placebo arm)	Relative reduction	Power (*)
Symptomatic infection rate	rate=27.8%	70%	81.5%
Peak TSS	CV=125%	65%	81.2%
VL-AUC	CV=91%	50%	84.8%
VLPEAK	CV=63.5%	40%	92.2%
TSS-AUC	CV=155%	80%	80.7%

(*) Power achieved with placebo and 60 Neumifil participants (alpha 0.05 1-sided).

CV = coefficient of variation.

Corresponding power calculations for the comparison of the placebo arm (40 participants) to one of the 2 Neumifil dose arms (30 participants) are provided below:

Endpoint	Assumption (placebo arm)	Relative reduction	Power (*)
Symptomatic infection rate	rate=27.8%	70%	66.6%
Peak TSS	CV=125%	65%	68.7%
VL-AUC	CV=91%	50%	72.8%
VLPEAK	CV=63.5%	40%	82.6%
TSS-AUC	CV=155%	80%	68.1%

(*) Power achieved with placebo and 30 Neumifil participants (alpha 0.05 1-sided).

CV = coefficient of variation.

9.3. Populations for Analyses

The study populations are defined in [Table 9-1](#).

Table 9-1: Study Populations

Population	Description
Enrolled	All participants who have been randomised. Potential participants who are screened for the purpose of determining suitability for the study, but do not participate in the study, are not considered enrolled, unless otherwise specified by the protocol.
Intent-to-treat (ITT) analysis set	All participants randomised, having received at least 1 dose of IMP, and challenged with the study virus.
Intent-to-treat infected (ITT-I) analysis set	All participants randomised, having received at least 1 dose of IMP, and challenged with the challenge virus, and who were infected with challenge virus as per the definition of laboratory-confirmed infection.
Per protocol (PP) analysis set	All participants randomised, having received the planned dose of IMP (Neumifil 3 doses on Days -3 to -1, 1 single dose of Neumifil on Day -3 followed by 2 doses of placebo on Days -2 and -1; or placebo 3 doses on Days -3 to -1, according to randomisation) and challenged with the study virus, who complete the quarantine period up to its planned final day (Day 8) and present no major deviation likely to impact the evaluation of the primary efficacy endpoint.
Safety analysis set	All participants randomised having received at least 1 dose of IMP. Participants will be analysed according to the intervention (multiple dose Neumifil, single dose Neumifil, placebo) they received.
PK analysis set	All participants randomised having received at least 1 dose of IMP, with at least 1 postdose PK result.

Membership of participants in each analysis set will be determined at a planned data review meeting, prior to any analysis and database lock.

The primary efficacy analysis will be on the PP analysis set. The ITT analysis set will be used for supportive analyses on all or part of the primary and secondary efficacy endpoints, as defined in the statistical analysis

plan (SAP). The safety evaluation will be performed on the safety analysis set. Additional analysis sets may be defined in the SAP.

9.4. Statistical Analyses

This section is a summary of the planned statistical analyses of the most important endpoints including primary and key secondary endpoints.

Data will be analysed and reported using SAS® version 9.4 or later.

9.4.1. Statistical Analysis Plan

The SAP will be developed and finalised prior to database lock for the study. The finalised SAP will be signed prior to unblinding the study data. The SAP will provide a more technical, detailed, and comprehensive description of the statistical analyses that will be computed, expanding on the protocol-specified analysis.

Any deviation(s) from the original statistical plan outlined in the protocol will be described and justified in an amendment to the protocol and/or SAP, as appropriate, and referenced in the final clinical study report.

Further post-hoc evaluations of any exploratory endpoints may be conducted and reported separately.

9.4.2. General Considerations

9.4.2.1. Descriptive Statistics

Continuous variables will be summarised using number of available data, number of missing data, mean (and/or geometric mean, where applicable), standard deviation, median, lower quartile, upper quartile, minimum, and maximum values. When relevant, confidence intervals (CIs) will be computed for the mean and/or the median.

Categorical variables will be summarised using number of available data, number of missing values, frequency counts for each category and corresponding percentage. Percentages will be calculated using the number of available data as the denominator (i.e., not including missing values). When relevant, CIs will be computed. If not otherwise specified in the SAP, the Wilson Score Method will be used to compute CIs for proportions.

9.4.2.2. Inferential Statistics and Significance Testing

Between-arm comparisons will be performed using appropriate hypothesis tests at the 5% 1-sided significance level, except if otherwise specified. No adjustment for multiple testing will be performed (see [Section 9.1](#), Statistical Hypothesis).

The main analyses will be the ones comparing the 2 active treatment arms pooled to the placebo arm. These analyses will be repeated with an exploratory purpose to the comparison of each Neumifil arm to the placebo.

For continuous variables (either raw data or log-transformed data) the difference in means, the standard error and the 90% and 95% 2-sided CIs will be presented. In case of log-transformed variables, in addition to the previous statistics on the log-transformed data, the geometric means and geometric mean ratio and

its 90% and 95% 2-sided CIs for the original variable will be presented. The Wilcoxon rank sum test, t-test, or analysis of covariance will be used, depending on whether the endpoints are normally distributed. Details on the method used for each endpoint will be provided in the SAP. Methods for checking statistical model assumptions and alternative methods of analysis if the assumptions are not fulfilled will be described in the SAP.

For categorical variables, differences in absolute frequency and/or relative risks will be presented, with their 90% and 95% 2-sided CIs. Except otherwise specified in the SAP, the Chi-square test (or Fisher exact test) will be used to compare frequencies between study intervention arms.

9.4.3. Planned Analysis

9.4.3.1. Participant Accountability

The number of participants receiving challenge agent, receiving IMP (Neumifil/placebo), withdrawing from (also split by reason for withdrawal), and completing the study, and the numbers in each analysis set, will be summarised.

9.4.3.2. Protocol Deviations

Participant's data will be reviewed for major protocol deviations prior to database lock at a planned data review meeting, and decisions will be documented within the meeting minutes. At this meeting, participants will be reviewed for their inclusion/exclusion from the analysis sets.

9.4.3.3. Demographic and Baseline Characteristics

Descriptive statistics of demographics (age, sex, height, body weight, BMI, and ethnicity) will be presented by study intervention arm (each individual dose arm, the pooled Neumifil arms, and the placebo arm) and across all participants. Medical history information will be listed. Other baseline characteristics will be defined in the SAP.

9.4.3.4. Compliance to Study Intervention

For each participant, the proportion of the planned dose actually received will be computed.

Compliance with IMP (Neumifil/placebo) will be computed for each study intervention arm as the proportion of participants actually receiving IMP as prescribed (i.e., 100% of the planned dose has been received).

9.4.4. Primary Efficacy Analysis

The primary efficacy analysis will be conducted on the per protocol (PP) analysis set ([Section 9.3, Populations for Analyses](#)).

For the symptomatic infection rate, the estimator with its 2-sided 90% and 95% CIs will be presented by treatment arm. The differences between the pooled active treatment arms and the placebo arm, and between each active treatment dose arm and the placebo arm, will be computed with their 2-sided 90% and 95% CIs. The 3 pairwise comparisons will use the Pearson Chi-square test, or the Fisher exact test if the assumptions for the Chi-square test are not met. Each test will use a nominal 1-sided type-one error of

0.05 without adjustment for multiplicity. In addition, the difference between the 2 Neumifil dose arms will be computed with its 90% and 95% CIs but no formal statistical test will be computed.

For the peak TSS, the mean and median and the 2-sided 90% and 95% CIs for the mean will be presented by treatment arm. The differences between the pooled active treatment arms and the placebo arm, and between each active treatment dose arm and the placebo arm, will be computed with their 2-sided 90% and 95% CIs. The 3 pairwise comparisons will use the Wilcoxon rank-sum test. Each test will use a nominal 1-sided type-one error of 0.05 without adjustment for multiplicity. In addition, the difference between the 2 Neumifil dose arms will be computed with its 90% and 95% CIs but no formal statistical test will be computed.

Further details on the primary efficacy analysis will be provided in the SAP.

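### Peak TSS is tested on ranks, but the only named between-arm estimate is a difference in means, so its confidence interval and the p-value can conflict

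*Combined protocol and SAP*

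**What the plan says.** Section 9.4.4 of the protocol, repeated in the synopsis, sets out three things for peak TSS.

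- **Arm summaries:** "For the peak TSS, the mean and median and the 2-sided 90% and 95% CIs for the mean will be presented by treatment arm". Medians are shown, but intervals are given for means only.
- **Between-arm estimates:** the differences of pooled Neumifil and of each dose arm from placebo "will be computed with their 2-sided 90% and 95% CIs". The type of difference is not named here. The general rule for continuous variables in Section 9.4.2.2 supplies it: "the difference in means, the standard error and the 90% and 95% 2-sided CIs will be presented".
- **Test:** "The 3 pairwise comparisons will use the Wilcoxon rank-sum test". "Each test will use a nominal 1-sided type-one error of 0.05 without adjustment for multiplicity".

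Section 9.2 powers the endpoint on a 65% relative reduction with a CV of 125%. "The number of 40 participants in the placebo arm and 60 (30 in each dose arm) in the pooled Neumifil group" are said to give at least 80% power.

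The text names no Hodges-Lehmann shift, Mann-Whitney probability or interval for a median difference. It does not say how to read the result if the interval and the p-value point different ways. Sections 9.4.2.2 and 9.4.4 leave further detail to a separate SAP, whose text is not in the available document.

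**The concern.** One limit of a 2-sided 90% interval corresponds to a 1-sided 0.05 test, so readers will naturally set the two side by side. Here they answer different questions. The interval concerns the difference in average peak score. The Wilcoxon test concerns whether participants in one arm tend to rank below those in the other. For a symmetric shift the two nearly coincide. For a skewed score with many low or zero values they need not.

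At stake is the reporting of a primary endpoint. The trial could show a significant p-value beside a 90% interval that includes zero, or a non-significant p-value beside one that excludes it. Either way, the published effect size would not be the effect that was tested.

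**Working it through.** **1. Inputs.** From Section 9.2: 40 placebo, 60 pooled Neumifil (30 per dose arm), 65% reduction, CV 125%, 1-sided 0.05. From Section 8.3.2: 11 items graded 0–3, with one extra grade for shortness of breath, so TSS is an integer from 0 to 10×3 + 4 = 34. Not in the documents, and therefore assumed: placebo mean peak TSS (3 to 5), share of placebo zeros (0–35%), distribution shape, variance in the active arms, and a t-based interval.

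**2. Reproduce the stated power.** Two-sample pooled t-test with common SD = 1.25 × placebo mean and difference = 0.65 × placebo mean:

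- 40 vs 60: noncentrality = 0.65 / (1.25 × √(1/40 + 1/60)) = 2.547; power 81.2%, as stated.
- 40 vs 30: noncentrality = 0.65 / (1.25 × √(1/40 + 1/30)) = 2.153; power 68.7%, as stated.

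The design calculation is therefore a t-test on means. Design and estimate concern means; only the test concerns ranks.

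**3. Why normality cannot be relied on.** With CV 125%, a normal model puts Φ(−1/1.25) = Φ(−0.8) ≈ 21% of placebo scores below zero. With the same SD and a 65% lower mean, it puts Φ(−0.35/1.25) = Φ(−0.28) ≈ 39% of active scores below zero. A score bounded at 0 with this CV must be markedly non-normal.

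**4. How often the two can conflict.** 10,000 simulated trials per scenario, 40 vs 60. A conflict is a trial in which the tie-corrected 1-sided Wilcoxon test at 0.05 and the 2-sided 90% pooled-variance interval for the mean difference give different answers.

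| Assumed scores | Mean reduction | Interval excludes 0 | Wilcoxon significant | Conflict |
|---|---|---|---|---|
| Normal, common SD | 65% | 81.6% | 79.9% | 5.2% |
| Lognormal | 65% | 99.3% | 100.0% | 0.7% |
| Negative binomial, equal CV, placebo mean 5 | 65% | 98.9% | 91.6% | 7.4% |
| Negative binomial, equal CV, placebo mean 3 | 65% | 99.0% | 89.5% | 9.5% |
| Negative binomial, about equal SD | about 65% | 88.5% | 100.0% | 11.5% |
| Zero-inflated, effect on incidence only | 65% | 91.5% | 99.4% | 8.0% |
| Zero-inflated, effect on severity only | 65% | 98.5% | 71.1% | 27.5% |
| Negative binomial | 50% | 85.7% | 64.9% | 22.6% |
| Negative binomial | 40% | 64.0% | 45.6% | 22.8% |
| Zero-inflated, severity only | about 35% | 52.6% | 27.5% | 26.5% |
| Zero-inflated, incidence only | about 31% | 37.7% | 56.6% | 22.2% |
| Negative binomial, no effect | 0% | 5.0% | 5.0% | 4.4% |

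A separate run gave about 5% (normal), 9% (negative binomial), 5% (incidence only) and 26% (severity only) at a 65% reduction, and 22–35% at 40–50% reductions. For 40 vs 30 at a 65% reduction, conflict ranged from 3% to 32%.

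Conflict runs both ways. Under a severity-only effect the interval excludes zero when Wilcoxon is not significant; under an incidence-only effect it is the reverse. A constructed stress case, with more participants mildly symptomatic but severity much lower, reached 59%. It is left out of the ranges quoted here.

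**5. Effect on power of keeping Wilcoxon.** Under the plan's normal, common-SD inputs, with asymptotic relative efficiency 0.955 (√0.955 = 0.977):

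- 40 vs 60: Φ(2.547 × 0.977 − 1.645) = Φ(0.844) ≈ 80.1% (simulated 79.9%).
- 40 vs 30: Φ(2.153 × 0.977 − 1.645) = Φ(0.459) ≈ 67.7% (simulated 67.3%).

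These are within 2 points of the stated 81.2% and 68.7%.

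**The case against.** The strongest reply is that nothing is left open. One test at one level is named in advance, and no sentence gives an interval a decision role. Section 9.4.4 asks for the same 90% and 95% intervals for the dose-versus-dose difference, where it plans no formal test, so the intervals plainly also have a descriptive purpose. This stands. A reader might infer that the mismatch lets the sponsor choose the favourable result; the documents do not support that, because the Wilcoxon test fixes the significance verdict.

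Second, Section 9.4.4 does not itself say difference in means and never calls it the primary estimate. It shows medians too, and a SAP signed before unblinding (Section 9.4.1) could still name a rank-based effect. This also stands, and it limits the point to the available text. It does not remove it: the only between-arm estimate named for continuous variables does not match the test.

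Third, a reader might infer that interval and test will often disagree. The figures do not carry that. At the design effect most assumed distributions give about 1–12%, some 5% is threshold noise that appears even for a normal shift, and the two point in opposite directions in at most 2% of trials. Only a severity-only effect, or a weaker true effect, takes conflict above 20%. Severity-only cannot be set aside, however, since the objective covers incidence and/or severity.

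Finally, means beside a rank test are common and readable. That argues for keeping the mean difference, not for leaving it as the only effect shown.

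**Conclusion.** The point holds as a mismatch between estimate and test on a primary endpoint, not as an open choice of test. Conflict is possible in roughly 1–27% of trials at a 65% reduction with placebo CV near 125%, and in about 20–35% at 30–50% reductions, for 40 versus 60. These ranges cover the scenarios tried and are not bounds. They rest on an assumed mean, share of zeros, shape, active-arm variance and interval method, none of which the documents give. That conflict can occur in both directions does not hinge on any one of these choices. The matter is modest in a proof-of-concept trial, but worth settling because it concerns a primary result and costs little.

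**What to change.** Keep the Wilcoxon rank-sum test as the deciding analysis. Before unblinding, add the following to Section 9.4.4 or the SAP:

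- For each of the three tested comparisons, report the Mann-Whitney probability that a Neumifil participant has a lower peak TSS than a placebo participant, counting ties as half, with 90% and 95% intervals. The estimate is the Wilcoxon statistic rescaled, with 0.5 meaning no difference. Name the interval method.
- Label the mean difference and its intervals as descriptive.
- State that the Wilcoxon result decides if the two appear to conflict.

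Replacing the primary test is not recommended. It would change the protocol's named analysis, which Section 9.4.1 requires to be described and justified in an amendment, and it is not needed to cure the mismatch.

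The cost is a little extra analysis and an effect measure less familiar to clinical readers. The planned numbers stay as they are.

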9.4.5. Secondary Efficacy Analysis

Secondary endpoints as outlined in [Section 3](#), Objectives and Endpoints, will be summarised by study intervention arm as described in [Table 9-2](#). Further details on the secondary efficacy analysis will be provided in the SAP.

Table 9-2: Methods for Analysis of Secondary Efficacy Endpoints

Endpoint	Analysis
TSS-AUC	Descriptive statistics for continuous variables by treatment arm (Section 9.4.2 , General Considerations). Inferential analysis: pairwise t-tests or Wilcoxon rank sum tests.
Peak viral load by qRT-PCR	Descriptive statistics for continuous variables (Section 9.4.2 , General Considerations). Inferential analysis: Wilcoxon rank sum test.
Peak daily symptom score	Descriptive statistics for continuous variables (Section 9.4.2 , General Considerations). No inferential analysis.
Number (%) of participants with grade 2 or higher symptoms, starting from Day 1 (am) up to planned discharge from quarantine (Day 8, am)	Descriptive statistics for categorical variable variables (Section 9.4.2 , General Considerations). Inferential analysis: pairwise Chi-square tests (or Fisher exact tests).
Duration of clinical symptoms: 1) any symptoms.	Descriptive statistics for continuous variables (Section 9.4.2 , General Considerations).
Duration of clinical symptoms: 2) TSS of 2 or more (with at least 2 systems)	No inferential analysis.

Duration of clinical symptoms: 3) grade 2 or higher symptoms	
Time to resolution from peak clinical symptoms	
Descriptive statistics for continuous variables (Section 9.4.2, General Considerations).
 
Kaplan Meier curves will be prepared.
 
No inferential analysis.

Area under the qRT-PCR viral load-time curve (VL-AUC)	
Descriptive statistics for continuous variables by treatment arm (Section 9.4.2, General Considerations). Inferential analysis: pairwise t-tests or Wilcoxon rank sum tests.

Area under the tissue culture viral load-time curve (VL-AUC)	
VLPEAK (qRT-PCR)	
VLPEAK (tissue culture)	
Duration of quantifiable influenza (qRT-PCR)	
Descriptive statistics for continuous variables (Section 9.4.2, General Considerations).
 
No inferential analysis.

Duration of quantifiable influenza (tissue culture)	
Duration of detectable influenza (tissue culture)	
Time to resolution from VLPEAK by qRT-PCR	
Descriptive statistics for continuous variables (Section 9.4.2, General Considerations).
 
Kaplan Meier curves will be prepared.
 
No inferential analysis.

Time to resolution from VLPEAK by quantitative viral culture	
Total weight of mucus produced	
Descriptive statistics for continuous variables (Section 9.4.2, General Considerations).
 
No inferential analysis.

Total number of tissues used	
Incidence of RT-PCR-confirmed influenza infection, defined as 2 quantifiable (\geq LLOQ) qRT-PCR measurements (reported on 2 or more independent nasal samples over 2 days)*	
Descriptive statistics for categorical variable variables (Section 9.4.2, General Considerations).
 
Inferential analysis: pairwise Chi-square tests (or Fisher exact tests).

Occurrence of at least 1 positive quantitative (\geq LLOQ) cell culture measurement in nasal sample	

Incidence of cell culture-confirmed symptomatic influenza infection	
Number (%) of participants with lab-confirmed infection and fever ($\geq 37.9^{\circ}\text{C}$)	

LLOQ = lower limit of quantification; (q)RT-PCR = (quantitative) reverse transcriptase polymerase chain reaction; TSS = total symptoms score; TSS-AUC = area under the curve over time of total symptoms score; VL-AUC = area under the viral load-time curve; VLPEAK = peak viral load.

* Additional sensitivity analyses using alternative definitions for symptomatic infections may be added in the Statistical Analysis Plan (SAP).

9.4.6. Tertiary/Exploratory Analysis

Tertiary/exploratory endpoints as outlined in [Section 3](#), Objectives and Endpoints, will be summarised by study intervention arm. Further details are described in the SAP.

9.4.7. Safety Analyses

All safety analyses will be computed on the safety analysis set.

Unless otherwise stated, safety endpoints will be presented in terms of descriptive statistics only.

Adverse events will be coded using the most current version of the Medical Dictionary for Regulatory Activities (MedDRA) and summarised descriptively by system organ class, preferred term, and study intervention arm for the number of AEs reported and the number and percentage of participants reporting each AE.

[REDACTED]

Further details on the safety analyses will be provided in the SAP.

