	To evaluate the effect of Neumifil in reducing the incidence of influenza infection due to influenza viral challenge, compared to placebo.	
 RT-PCR-confirmed influenza infection, defined as 2 quantifiable (\geq lower limit of quantification [LLOQ]) qRT-PCR measurements (reported on 2 or more independent nasal samples over 2 days), starting from Day 1 (pm) up to planned discharge from quarantine (Day 8, am). Occurrence of at least 1 positive quantitative (\geq LLOQ) cell culture measurement in nasal samples, starting from Day 1 (pm) up to planned discharge from quarantine (Day 8, am). Culture lab-confirmed symptomatic influenza infection, defined as: 
 Lab-confirmed culturable influenza infection (1 quantifiable [\geq LLOQ] cell culture measurement, starting from Day 1 [pm] up to planned discharge from quarantine [Day 8, am]), 
AND
 
 Any symptoms of grade ≥ 2 at a single time point. 
Further sensitivity analysis may be performed on the above qRT-PCR-related endpoints where detection by qRT-PCR is reported above the LLOD instead of the LLOQ and/or using other definitions for the symptomatic component. Details will be provided in the statistical analysis plan (SAP).
 Number (%) of participants with lab-confirmed infection and fever ($\geq 37.9^{\circ}\text{C}$).
	Safety	
	To evaluate the safety of intranasal doses of Neumifil, compared to placebo.	
 Occurrence of AEs (solicited and unsolicited) up to the Day 28 (± 3 days) follow-up visit, including any SAEs. Occurrence of unsolicited AEs of special interest (AESIs) up to the Day 28 (± 3 days) follow-up visit. AESIs are: clinically significant reduction in FEV₁ and FVC.

	Objective(s)	Related Endpoints/Outcome Measure(s)
	To monitor the safety of the challenge virus.	
 • Occurrence of unsolicited AEs related to virus challenge from Day 0 up to planned discharge from quarantine (Day 8, am). • Occurrence of unsolicited SAEs related to virus challenge from Day 0 up to planned discharge from quarantine (Day 8, am). • Use of concomitant medications from Day 0 up to the Day 28 (± 3 days) follow-up visit.
Tertiary / Exploratory*:	To explore Neumifil concentrations in blood (single and multiple doses).	Neumifil concentrations will be explored in blood.

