4.1. Overall Design

This is a single-centre, randomised, double-blind, placebo-controlled, proof-of-concept Phase 2 study in healthy adult male or female participants aged between 18 and 55 years old, inclusive, utilising:

- Investigational medicinal product (IMP) (active): Neumifil, [REDACTED] once daily for 3 days on Days -3 to -1 (multiple dose active treatment) or [REDACTED] single dose on Day -3 (single dose active treatment), intranasally administered ([REDACTED] Neumifil [REDACTED])
- IMP (placebo): Matching placebo, once daily for 3 days on Days -3 to -1 (placebo treatment) or once daily for 2 days on Days -2 and -1 (single dose active treatment), intranasally administered [REDACTED]
- Challenge agent: influenza A/Perth/16/2009 (H3N2) virus challenge strain, $\sim 10^{5.5}$ tissue culture infective dose (50%) (TCID₅₀), intranasally administered.

The primary goal of this Phase 2 study is to assess the pre-exposure prophylactic antiviral activity against influenza, safety, and tolerability of Neumifil via a human viral challenge model.

Each participant will receive one of 3 treatments:

- Neumifil once daily for 3 days on Days -3 to -1 (multiple dose active treatment).
- A single dose of Neumifil on Day -3 and placebo once daily on Days -2 and -1 (single dose active treatment).
- Placebo once daily for 3 days on Days -3 to -1.

A total of up to evaluable 100 participants is planned to be enrolled in this study: 30 participants on multiple dose active treatment, 30 participants on single dose active treatment, and 40 participants on placebo.

The expected duration of study participation for a participant is 4 months, with the following sequence and duration of study phases:

- **Screening phase:** From Day -93 to Day -5 (prior to quarantine admission). Historical generic screening data collected through the hVIVO generic screening process may be transferred to this study after the study-specific consent form has been signed by the participant.
- **Inpatient phase:** Participants will be resident in the quarantine unit for approximately 13 days (from Day -4 to Day 8). Procedures will include:
 - **Pre-human viral challenge:**
 - Admission to quarantine unit on Day -4.
 - Baseline assessments and randomisation will be conducted as per Schedule of Events (SoE) up to Day -3, predose.
 - Administration of Neumifil and/or placebo once daily on Days -3 to -1, according to randomisation.
 - **Human viral challenge:**

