 - Influenza virus inoculation on Day 0.

- **Post-human viral challenge:**
 - Day 1 onwards and each day – study assessments will be conducted as per SoE.
 - Discharge from the quarantine unit on Day 8 [REDACTED]
[REDACTED]
[REDACTED]
- **Outpatient phase:**
 - Final follow-up visit: Day 28 (±3 days).

Study assessments will be conducted as per SoE

The Study Schematic, showing participant progression through the study, is presented in [Section 1.1](#), Study Schematic: On-study Participant Progression. The SoE is presented in [Section 1.2](#), Schedule of Events.

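### Challenge-virus safety percentages use a denominator that does not require inoculation, so they would be understated if anyone is dosed but not challenged

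*Combined protocol and SAP*

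**What the plan says.** Section 9.4.7 assigns one population to all safety work: "All safety analyses will be computed on the safety analysis set". Table 9-1 in Section 9.3 defines that population as "All participants randomised having received at least 1 dose of IMP. Participants will be analysed according to the intervention" received. Receipt of the challenge virus is not a condition.

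Section 3 has two safety objectives, one for Neumifil and one for the challenge virus. Under the second it lists "Occurrence of unsolicited AEs related to virus challenge from Day 0 up to planned discharge from quarantine (Day 8, am"), the matching SAE endpoint, "Occurrence of unsolicited SAEs related to virus challenge from Day 0 up to planned discharge from quarantine (Day 8, am"), and use of concomitant medication from Day 0 to the Day 28 visit.

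The two exposures start on different days. Section 4.1 gives "Administration of Neumifil and/or placebo once daily on Days -3 to -1, according to randomisation" and then "Influenza virus inoculation on Day 0".

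Elsewhere the protocol treats dosed and challenged as different groups. The ITT set in Table 9-1 is "All participants randomised, having received at least 1 dose of IMP, and challenged with the study virus". Section 9.4.3.1 will summarise "The number of participants receiving challenge agent, receiving IMP (Neumifil/placebo), withdrawing from" the study, so it counts the two exposures separately.

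**The concern.** The safety set suits the Neumifil objective, because exposure to IMP defines it. For the virus objective, the people at risk are those who were inoculated. Someone who leaves between the first dose on Day -3 and inoculation on Day 0 cannot have a virus-related AE or SAE, yet remains in the denominator as a non-event.

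The protocol leaves several routes to that position:

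- Table 7-2 allows withdrawn participants to be replaced. A participant who was dosed and then withdrew, and the replacement, would both meet the safety-set definition.
- Status 3 of Table 7-1 halts virus administration after an unexpected virus-related event. Anyone already dosed and awaiting inoculation would then be in the set without exposure.
- In the first-in-human study (Section 2.1.2.2), one participant was withdrawn after a fall in FEV1 and FVC following the first dose.

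At stake is how accurately the percentages with virus-related events are reported. If the unchallenged participants were unevenly spread across arms, the percentages could also differ between arms with no real difference behind them.

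**Working it through.** **Who is in each set (Table 9-1)**

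| Set | At least 1 IMP dose | Challenged |
|---|---|---|
| Safety | required | not required |
| ITT | required | required |

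The difference between the two memberships is exactly the group dosed but not challenged. No set meant for safety requires challenge.

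**Is there a denominator rule that removes them?** Section 9.4.2.1 excludes only missing values from percentages. A participant with no virus-related AE reads as a non-event rather than clearly as missing, so this rule does not settle the matter.

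**Formula.** Let x participants have a virus-related AE among n challenged, and let k be dosed but not challenged.

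- Rate among those exposed: p = x/n
- Reported rate: x/(n + k) = p × (1 − u), where u = k/(n + k)

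The relative understatement is therefore u, whatever the value of p.

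**Inputs.** The protocol gives neither u nor an expected virus-related AE rate, so there is no figure of its own to reproduce on this point. I assume u = 0, 2, 5 and 10%. For p, I use 27.8%, which is the placebo symptomatic infection rate assumed in Section 9.2 and serves here only as an illustration, and 10% to represent a rarer event.

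| u | p = 27.8% reported as | points lost | p = 10% reported as | points lost |
|---|---|---|---|---|
| 0% | 27.8% | 0 | 10.0% | 0 |
| 2% | 27.2% | 0.6 | 9.8% | 0.2 |
| 5% | 26.4% | 1.4 | 9.5% | 0.5 |
| 10% | 25.0% | 2.8 | 9.0% | 1.0 |

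**Unequal arms.** Take the same true rate in both arms, 30 challenged in a dose arm plus k unchallenged, against an arm with none unchallenged.

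- k = 2, p = 27.8%: 27.8 × 30/32 = 26.1%, a spurious gap of 1.7 points
- k = 3, p = 27.8%: 27.8 × 30/33 = 25.3%, a gap of 2.5 points
- k = 3, p = 10%: 3/33 = 9.1%, a gap of 0.9 points

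If the shares are equal there is no gap: 3 on top of 30 and 4 on top of 40 both give u = 9.1%.

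**Concomitant medication.** An unchallenged participant can still take medication after Day 0, so the formula does not apply as it stands. The percentage would mix people with and without virus exposure, and the direction of the effect is not fixed.

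**What is not touched.** The powers in Section 9.2 concern efficacy endpoints and do not involve the safety set. With a one-sided 0.05 pooled-variance normal approximation, the symptomatic infection figures reproduce: 81.5% for 40 versus 60 and 66.6% for 40 versus 30.

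**The case against.** The strongest reply is that the operative detail may simply not be visible. A redacted block follows the AE-summary paragraph in Section 9.4.7, that section defers further detail to the SAP, and Section 9.3 allows the SAP to define more analysis sets. This stands as a caveat. The legible sentence nevertheless covers all safety analyses without exception, and nothing readable limits the virus endpoints to inoculated participants.

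The second reply is about size, and most of it stands. The window is three days, in resident quarantine, with supervised dosing. The virus objective is to monitor, without a comparison with placebo, and safety is descriptive unless otherwise stated. AE counts are unaffected, and because the number challenged is reported separately, a reader could recompute the rate. For SAEs, Section 2.1.1 reports none related to the virus in over 400 inoculations; zero events give 0% under either denominator.

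A reader might infer that unchallenged participants will arise mainly in the Neumifil arms, so that the drug will appear to reduce virus-related events. The documents do not support that:

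- The first-in-human withdrawal is a single case, described as a one-off with an unusual time-course, and gives no rate.
- The discontinuation criteria are redacted.
- The ITT definition allows challenge after only one dose, so an incomplete IMP course need not mean no inoculation.
- Replacement is discretionary, and barred for withdrawals under the stopping rules.

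Imbalance is possible, but neither its presence nor its direction can be established.

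**Conclusion.** The mismatch between population and endpoint is in the text. Its effect is conditional. A reader might take the rule to mean that virus-related rates are diluted in this trial; that follows only if at least one participant is dosed and not inoculated, and the protocol gives no such number.

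For an assumed unchallenged share of 2 to 10%, virus-related AE percentages would be understated by 2 to 10% in relative terms, or 0.6 to 2.8 points at the illustrative 27.8% and less for rarer unsolicited events. A halt of inoculation under Table 7-1 could take the share outside that range, but nothing in the documents allows it to be sized.

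Only descriptive percentages are affected. Event counts, tests, power, the primary analysis and the stopping rules are not. This is a reporting-denominator issue and has no bearing on clinical management. It is a minor improvement worth making, provided the redacted part of Section 9.4.7 does not already make it.

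**What to change.** In Section 9.4.7 and the SAP, replace the single-population sentence with wording to this effect: Neumifil safety analyses use the safety analysis set; the challenge-virus safety endpoints (virus-related AEs, virus-related SAEs and concomitant medication from Day 0) use the safety-set participants who received the challenge virus, grouped by IMP received.

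This subset has the same membership as the ITT set, so a denominator note is enough and a new row in Table 9-1 is optional. The current safety set stays as it is for Neumifil. If the redacted text already makes this restriction, only the opening sentence of Section 9.4.7 needs to be aligned with it.

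The cost is one sentence and one flag, derived from the inoculation time that Section 6.2.2 already requires to be recorded. No procedure or sample size changes. The downside is a second denominator in the safety tables, which the table headers should label clearly. Section 9.4.1 has the SAP signed before unblinding, so the change should be made by then.
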